14.2.3 Data Review and Clarification Procedures

By electronically signing the eCRF with an automated time stamp, the investigator will confirm that all investigations have been completed and conducted in compliance with the CSP and that reliable and complete data have been entered into the eCRF.

All data required by this CSP are to be recorded in the eCRF as soon as possible. However, direct entries are not allowed; data must be transcribed from the source documentation (e.g., subject file, scales) to the eCRF.

All data required by this study protocol, except photography ratings CCI, are to be entered into a sponsor-validated database of eCRFs.

If corrections are necessary, an authorized member of the investigator's study personnel will enter the correct data into the web-based eCRF. The audit trail in the EDC system documents all changes.

The data management CRO and sponsor's data management function will be responsible for data processing, in accordance with the CRO's and sponsor's data management procedures. Database close will occur only after quality assurance procedures have been completed.

Entries from questionnaires completed by the subject will be entered into the eCRF by study personnel. If corrections in the questionnaires are necessary, the subject should be instructed to make a correction by drawing only a single line through the error, leaving the incorrect entry legible. The subject should date and initial the correction. The investigator should not make any changes to these documents.

14.2.4 Auditing

To ensure compliance with applicable standards and regulations, the sponsor, IEC/IRB, or regulatory authorities may conduct a quality assurance assessment or audit of site records at any time during or after completion of the study. In the event of an audit, investigators must grant access to all relevant documents (including source documents, electronic records, and other applicable study documentation) and provide support at all times for auditing activities.

14.3 Record Retention

Essential documents should be retained per applicable regulations and as instructed by the study sponsor. Essential documents at the investigational site include but are not limited to:

- Source documentation (e.g., subject files);
- Subject identification code list (i.e., provided by template to the investigator, along with the Investigator Site File, at the beginning of the investigation), which identifies the subject by number, name, and date of birth;
- A copy of the study protocol and any amendments;

- A CD/DVD with eCRF data and any associated subject-related source data (or, where applicable, authorized copies of source data);
- Signed ICFs;
- Copies of site investigators' and co-workers' curricula vitae;
- Copies of all direct correspondence with the IEC/IRB and with the regulatory authority(ies);
- Copies of all relevant correspondence between the investigator and the monitor, and between the investigator and the sponsor;
- Copies of any photographs;
- Copies of IMD receipt forms and device inventory forms; and
- Copies of safety information reported during the investigation and submitted by the sponsor.

Study documents may not be destroyed by study-site personnel prior to the end of the required retention period as specified by local regulations. The investigator or the institution must inform the sponsor in due time if the investigator leaves the institution during the retention period. This rule also applies when the institution closes within the retention period.

Upon closure of the study, the investigator must maintain all study-site records in a safe and secure location. The investigator is responsible for the integrity, retention, and security of all study-related records. The investigator must ensure that any reproductions of the original records are legible and provide a true and accurate copy of the original. Accurate, complete, and current records must be stored in such a way as to permit easy and timely retrieval for the sponsor or any applicable regulatory authorities.

The sponsor will inform the investigator of the time period for retaining these records to comply with all applicable regulatory requirements, with the minimum retention time being the longest of those times dictated by institutional requirements, local laws or regulations, or the sponsor's standard procedures. The investigator must notify the sponsor in the event of any changes to archival arrangements due to withdrawal of the investigator's responsibility for keeping study records to ensure that suitable arrangements for the retention of study records are made.

14.4 Publication Policy

The results of this study and any discoveries related to this study, regardless of whether they have technical or medical character, are the property of the sponsor.

The CSP, study data, and information related to the study or the sponsor's products or research programs are to be kept confidential and may not be disclosed without the consent of the sponsor.

The investigator agrees that the results of this study may be used for submission to national or international registration and supervising authorities. The sponsor may disclose the information obtained during the study to regulatory authorities or other personnel as required. If necessary, the sponsor may disclose the names, contact information, and qualifications of all investigators as well as their roles in the study. Upon completion of the study, publication or disclosure of the study results is to follow the terms contained in the sponsor's SOP.

The sponsor will ensure that a description of this clinical study is registered, and study results are disclosed on <http://www.ClinicalTrials.gov>, as required by US law. Study registration may include a list of study sites, as applicable.

14.5 Financial Disclosure

The US FDA Financial Disclosure by Clinical Investigators (21 CFR 54) regulations require sponsors to obtain certain financial information from investigators participating in covered clinical studies. By participating in the study, the investigator agrees to provide the required financial information and to promptly update the sponsor with any relevant changes to this financial information throughout the course of the study and for up to one year after its completion if necessary.

14.6 Investigator Compliance

The investigator will conduct the study in compliance with the protocol provided by the sponsor and in accordance with all relevant regulatory guidelines and requirements.

Modifications to the protocol should not be made without the agreement of the investigator and sponsor. The sponsor will submit all protocol modifications to the appropriate regulatory authority in accordance with applicable regulations. All protocol modifications require written IEC/IRB approval/favorable opinion, except in the case of an immediate hazard to subjects.

If an immediate deviation from the protocol is required to eliminate an immediate hazard to subjects, the investigator must contact the sponsor or assigned CRO, if possible, to discuss the planned course of action. The investigator must thoroughly document any departure from the protocol and submit appropriate documentation to the sponsor without delay.

16 APPENDICES

## List of Abbreviations

AE	Adverse Event
AEH	Average eyebrow height
ATC	Anatomical Therapeutic Chemical classification system of the World Health Organization
BMI	Body Mass Index
CI	Confidence interval
COVID-19	Coronavirus disease 2019
CRO	Contract Research Organization
CCI	
DRM	Data Review Meeting
FACE-Q™	Set of subject-reported questionnaire modules
FST	Fitzpatrick skin type
CCI	
ITT	Intent-to-Treat population
MedDRA	Medical Dictionary for Regulatory Activities
MEH	Maximum eyebrow height change
PP	Per Protocol Population
PROC MI	SAS multiple imputation procedure
PT	Preferred term
SAE	Serious Adverse Event
SAP	Statistical Analysis Plan
SAS	Statistical Analysis System®
CCI	
SOC	System organ class
SP	Safety Population
SSQ	Subject-Satisfaction Questionnaire
TC	Telephone contact
TEAE	Treatment-Emergent Adverse Event
TESAE	Treatment-Emergent Serious Adverse Event
TFL	Tables, Figures, and Listings
VAS	Visual analogue scale
WHO-DD	World Health Organization Drug Dictionary

## 1 General and Technical Aspects

The objective of this statistical analysis plan (SAP) is to specify the statistical analyses with appropriate detail and precision to serve as a guideline for statistical programming and creation of tables, figures, and listings for clinical study protocol M960101001, dated 16-NOV-2021, version 6.0 (Amendment 5).

All programs will be written using SAS version 9.4 or higher. A preferred font size of 9 points, minimum font size of 8 points with a unique font size for the whole document required will be used for the tables and figures in Section 14. For listings, a standard font size of 9 points will be used to produce the output in A4 format. Individual SAS programs will be written for all tables, figures, and listings. All outputs will be transferred into PDF. These PDF files will be generated as needed to populate the subsections of Section 14 and Section 16.2 for the clinical study report. Each output file will include the corresponding table of contents, preceding the content of the file.

The Merz standard Tables, Figures, and Listings (TFLs) for medical devices, version 2.0, dated 18-Feb-2020, will be applied and adapted to study specific requirements as laid down in the clinical study protocol and any amendments. These mock TFLs will serve as study-specific output specifications for statistical programming.

Special attention will be paid to planning and performance of quality control measures. Risk scores based on assessments of complexity and impact of errors and quality control measures for statistical programming (including analysis datasets, TFLs) will be documented in the quality control plan for the creation of statistical output.

## 2 Clinical Trial Design and Objectives

### 2.1 Clinical Study Design

This is a 180-day, prospective, evaluator-blind, multicenter, staged, confirmatory study designed to evaluate the safety and effectiveness of the Octave System in lifting the brow and improving the appearance of the face and neck. Approximately 50 subjects will be enrolled at up to five investigational sites in the United States.

All Fitzpatrick skin types (FST) will be eligible for study enrollment. It is estimated that approximately 85% of the total sample size will consist of subjects with a FST I, II, or III, and approximately 15% of subjects will be FST IV, V, or VI. Subjects enrolled will be healthy male or female subjects, aged 35 to 65 years at the time of screening, with mild to moderate eyebrow/upper-face laxity and fine lines, wrinkles, and laxity of the mid- to lower face and neck that are amenable to improvement with non-invasive intervention and are not severe enough for surgical intervention.

In this non-comparative, staged, confirmatory study, investigators and subjects will not be blinded to treatment, subjects will not be randomized, and all enrolled subjects will receive a single Octave-Ultherapy treatment of the brow, upper, mid, and lower face, and neck. Subjects in Stage 1 (n = 10) will receive treatment with one transducer **CCI** at energy level 4 and one transducer **CCI** at energy level 2. Remaining subjects in Stage 2 will receive treatment with three transducers **CCI** at energy level 4 and one transducer **CCI** at energy level 2. In Stage 1, an initial cohort of subjects will be enrolled, safety data will be assessed to Day 14, and subjects will participate until study end at Day 90 or Day 180 if reconsented for extended participation. In Stage 2, all enrolled subjects will be followed for 180 days. In addition, to reduce potential bias associated with using only treated-subject photographs for evaluation, photographs of approximately 25 untreated individuals, who meet selected appearance criteria, will be collected at two different time points and subsequently paired for evaluation by the independent, blinded

evaluators. Using this 2:1 ratio of treated subjects to untreated individuals, image sets of these untreated individuals will be randomly distributed among the pre- and post-treatment image sets of the treated subjects and presented to the blinded evaluators. For the primary effectiveness endpoint, the “baseline” photograph will be identified as “Photograph 1”, and the independent evaluators will be blinded to the randomly distributed treated versus untreated status of the comparator Photograph 2 (i.e., Day 90 post-treatment among treated subjects or post-baseline for untreated individuals). The same photographic assessment will be used for the secondary effectiveness endpoint with the comparator Photograph 2 collected at Day 180 post-treatment.

Study subjects will have approximately 4 on-site study visits, including screening, baseline/treatment, a Day 90 ( $\pm$  7 days) post-treatment visit, and a Day 180 ( $\pm$  14 days) post-treatment visit. Follow-up telephone calls (TCs) will occur at 3 days ( $\pm$  1 day), 14 days ( $\pm$  3 days), 28 days (+ 3 days), 120 days ( $\pm$  7 days), and 150 days ( $\pm$  7 days) after Octave-Ultherapy treatment. The primary effectiveness endpoint, the proportion of treated subjects with eyebrow lift, will be evaluated using a blinded, independent assessment of photographs at post-treatment Day 90 compared to baseline. Lift is concluded if at least two of three independent, blinded evaluators report “eyebrow lift” in the Day 90 standardized, photographic images when compared to baseline photographic images.

Secondary effectiveness evaluations will include a qualitative assessment of improvement in eyebrow lift at Day 180, as well as Day 90 and Day 180 evaluations of quantitative measurement of eyebrow lift and change from baseline in three FACE-Q modules (i.e., Satisfaction with Forehead and Eyebrows, Satisfaction with Lower Face and Jawline, and Patient-perceived Age visual analogue scale (VAS)).

Standard safety evaluations, including the incidence of adverse events (AEs) and serious adverse events (SAEs), will be assessed.

## 2.2 Clinical Study Objectives

Primary objective: To demonstrate the effectiveness and safety of the Octave System to lift the eyebrow.

Secondary objective: To demonstrate the effectiveness and safety of the Octave System to improve the appearance of the face and neck.

## 3 Determination of Sample Size

A responder rate of 72% is assumed for the proportion of subjects with eyebrow lift from baseline to Day 90, as defined by the correct selection of the Day 90 standardized, photographic images by two of three independent, blinded evaluators in the previous Ulthera System eyebrow clearance study (K072505). Monte-Carlo simulations were conducted to obtain sample sizes of evaluable subjects required to achieve an improvement rate (i.e., eyebrow lift reported by two of three independent, blinded evaluators) of  $\geq$  65% and lower bound of 1-sided 95% confidence interval (CI) above 50%. To achieve this threshold with  $\geq$  85% power, a sample size of 40 evaluable subjects will be required. Assuming a maximum attrition of 10 subjects, approximately 50 subjects will be enrolled. In Stage 1, 10 subjects will be enrolled, while all other subjects will be enrolled in Stage 2. Because a sample size of 40 subjects who complete the full Ultherapy treatment session is required, study enrollment will continue until the required number of treated subjects is achieved.

## 4 Analysis Sets

The following analysis sets will be defined for the statistical analysis of this clinical study:

## 4.1 Safety Population (SP)

The Safety Population (SP) includes all subjects who are enrolled and are treated with the Octave System.

## 4.2 Intent-to-Treat Population (ITT)

The Intent-to-Treat population (ITT) consists of all subjects who are enrolled.

## 4.3 Per Protocol Population (PP)

The Per Protocol population (PP) consists of all subjects in the ITT population who complete the full Ultherapy treatment session using the Octave System and do not have a major protocol violation. Major protocol deviations will be defined during the Data Review Meeting (DRM).

# 5 Endpoints for Analysis

## 5.1 Effectiveness Endpoints

### 5.1.1 Primary Effectiveness Endpoint

The primary endpoint of the study is the proportion of treated subjects with eyebrow lift, as demonstrated by comparing photographs taken at Day 90 (post-treatment) with baseline (pre-treatment) photographs. If the subject's screening photograph (Visit 1) is deemed acceptable upon review by the central photography vendor, it will default to the baseline (pre-treatment) photograph and will be used for reference throughout the study.

[figure not shown]
- Lift is concluded if at least two of three independent, blinded evaluators report "eyebrow lift" in the Day 90 standardized, photographic images when compared to baseline photographic images.
- The success criterion is defined by achieving simultaneously a point estimate  $\geq 65\%$  and a lower bound of the one-sided 95% Wilson confidence interval  $> 50\%$  for the proportion of subjects with eyebrow lift.

### 5.1.2 Secondary Effectiveness Endpoints

- Proportion of treated subjects with eyebrow lift, as demonstrated by comparing photographs taken at Day 180 (post-treatment) with baseline (pre-treatment) photographs.
- Proportion of treated subjects with eyebrow lift of at least 0.5 mm on frontal 2D photographs at Day 90 and Day 180 compared to baseline.
- Change from baseline in FACE-Q Satisfaction with Forehead and Eyebrows score (Rasch-transformed) at Day 90 and Day 180, as assessed by the subject.
- Change from baseline in FACE-Q Satisfaction with Lower Face and Jawline score (Rasch-transformed) at Day 90 and Day 180, as assessed by the subject.
- Change from baseline in FACE-Q Patient-perceived Age Visual Analogue Scale (VAS) rating at Day 90 and Day 180, as assessed by the subject.

CCI

CCI

[figure not shown]

## 5.2 Safety Endpoints

### 5.2.1 Secondary Safety Endpoint

- Incidence of treatment-emergent adverse events (TEAEs) related to Octave-Ultherapy treatment, as reported throughout the study.

CCI

CCI

## 6 Statistical Analysis Methods

Adequate descriptive statistics will be provided for each effectiveness and safety evaluation. Continuous variables (values and changes from baseline) will be summarized by number of observed values (n obs), number of missing values (n miss), number of imputed values (n imp, where applicable), mean, standard deviation, median, quartiles, minimum and maximum (i.e., metric statistics). Mean, quartiles, and median will be reported to one decimal place more than the data were collected, for the standard deviation two decimal places more will be displayed; for derived data, the number of decimal places will explicitly be given in the sections below.

Categorical variables will be summarized by frequencies and percentages (n, %) per category where the denominator will be chosen according to the adequate analysis population (i.e., frequency statistics). Frequency tables will include the number of missing values. Percentages will be calculated using the denominator of all subjects in a specified population. Percentages will be calculated using the number of subjects with non-missing data at the corresponding visit as denominator (observed cases). The denominator will be specified in a footnote to the tables for clarification if not otherwise obvious. Percentages will be reported to one decimal place.

Ordered categorical data will be summarized by quantitative and frequency statistics.

Shift tables, confidence limits (95%, two-sided), and descriptive p-values will be given, where appropriate.

Due to the COVID-19 pandemic outbreak, onsite visits might not be performed or only performed as virtual contact. In such cases, quantitative evaluations/assessments will not be performed.

CCI

### 6.1 Effectiveness Endpoints

Unless otherwise specified, all effectiveness endpoints will be summarized for the ITT population.

#### 6.1.1 Primary Effectiveness Endpoint

##### 6.1.1.1 Primary analysis

The primary endpoint of the study is the proportion of treated subjects with eyebrow lift by comparing photographs taken at Day 90 (post-treatment) with baseline (pre-treatment) photographs.

Each independent evaluator will assess “Eyebrow Lift”, “No Eyebrow Lift” or “Cannot Evaluate” between Photograph 1 (baseline) and Photograph 2 (post-baseline). Photograph 1 will be identified, and the independent evaluators will be blinded to the random distribution of treated versus untreated status of the comparator Photograph 2 (i.e., Day 90 post-treatment among treated subjects or post-baseline for untreated individuals). Lift will be declared if at least two blinded evaluators indicate “Eyebrow Lift” for the comparator photograph. In case at least two evaluators declare a photograph as not assessable (i.e., “Cannot Evaluate” is ticked), the corresponding lift score over all evaluators will be set to missing for the primary analysis. In case one evaluator rates a photograph as “Cannot Evaluate” and the other two evaluators disagree, the overall lift score will be set to “No Lift”.

The point estimate for the proportion of subjects fulfilling the primary endpoint will be described by frequency statistics for the ITT subset.

[figure not shown]
Effectiveness is established if:

[figure not shown]
- A. the point estimate is  $\geq 65\%$  and
- B. the lower bound of the one-sided 95% Wilson CI is  $> 50\%$ .

In addition, the proportion of untreated individuals fulfilling the primary endpoint will be calculated. It is expected that the point estimate for the proportion of untreated individuals is  $< 50\%$ .

Missing data, including a missing primary endpoint assessment in subjects with unacceptable (i.e. unassessable) or missing photographs at baseline or Day 90, will be imputed by multiple imputation. In case of complete data, no multiple imputation will be performed and the primary analysis is based on complete data for the ITT.

Imputation is done 50 times using a fully conditional specification logistic regression method, as implemented in SAS PROC MI with statement FCS LOGISTIC, and will use the investigational site and the baseline characteristics age and BMI as independent variables.

In a first step a total of  $m=50$  imputed datasets will be generated, where missing data in the primary endpoint (lift over all evaluators) is modelled via logistic regression based on input variables site, age and BMI at baseline. 

  response is coded as ("no lift", "lift"). The lower bound of the one-sided 95% Wilson CI ([WL, WU]) will be calculated using the following steps, as detailed in [1]:

1. The mean sample response  $\hat{p}_{Imp}$  and sample variance  $\hat{U}_{Imp}$ ,

$$\hat{U}_{Imp} = \frac{\hat{p}_{Imp} (1 - \hat{p}_{Imp})}{n},$$

will be calculated for each of the  $m=50$  imputed datasets with sample size  $n$ .

2. The overall mean  $\bar{p}_m$  and variance  $\bar{U}_m$  over all imputed datasets will be calculated:

$$\bar{p}_m = \frac{1}{m} \sum_{Imp=1}^m \hat{p}_{Imp},$$

$$\bar{U}_m = \frac{1}{m} \sum_{Imp=1}^m \hat{U}_{Imp}.$$

These will be used to obtain  $B_m$ ,

$$B_m = \frac{1}{m-1} \sum_{Imp=1}^m (\hat{p}_{Imp} - \bar{p}_m)^2,$$

the between-sample variance.

3. The lower boundary of the one-sided 95% Wilson CI (WL and WU) will be calculated as

$$\left[ \frac{2\bar{p}_m + \frac{t^2}{n} + \frac{t^2 r_m}{n}}{2 \left( 1 + \frac{t^2}{n} + \frac{t^2 r_m}{n} \right)} - \sqrt{\frac{\left( 2\bar{p}_m + \frac{t^2}{n} + \frac{t^2 r_m}{n} \right)^2}{4 \left( 1 + \frac{t^2}{n} + \frac{t^2 r_m}{n} \right)^2} - \frac{\bar{p}_m^2}{1 + \frac{t^2}{n} + \frac{t^2 r_m}{n}}} \right],$$

where  $t$  denotes the 0.95 quantile of the t-distribution with degrees of freedom  $\nu$ ,

$$\nu = (m - 1) \left( 1 + \frac{1}{r_m} \right),$$

and with

$$r_m = \left( 1 + \frac{1}{m} \right) \frac{B_m}{U_m}.$$

The study is considered successful, and consequently effectiveness is established, if the parameter estimate  $\bar{p}_m \geq 65\%$  (condition A), and the lower limit of the one-sided 95% Wilson CI exceeds the margin of 50% (condition B).

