## **6.4 Special Statistical/Analytical Issues**

### **6.4.1 Discontinuations and Missing Data**

#### **Independent Photographic Review for Eyebrow Lift at Day 90 and Day 180**

For analysis of the primary and secondary effectiveness endpoints regarding Independent Photographic Review for Eyebrow lift, the following procedure for incomplete data from the independent evaluators will be applied:

[figure not shown]
- If data from all three independent evaluators is missing, the outcome of the subject will be set to missing.
- If the result of two out of three evaluators is missing, the outcome of the subject will be set to missing.

- If the result of one evaluator is missing and the other two evaluators agree on the assessment “Eyebrow Lift” then the outcome of the subject is set to “lift” for all analyses.
- If the result of one evaluator is missing and the other two evaluators agree on the assessment “No Eyebrow Lift” then the outcome of the subject is set to “no lift” for all analyses.
- If the result of one evaluator is missing and the other two evaluators disagree, then the outcome of the subject will be set to missing.

For treated subjects with missing outcome, the multiple imputation technique will be employed as described above for the primary and secondary analyses. For the worst case analysis, these subjects will be analyzed as having “no lift”.

All other effectiveness data will be analyzed as observed with no imputation of missing values. The denominator for percentages will be all subjects in the respective analysis set or population (i.e., missing data for binary or categorical variables will be presented as a separate possible category ‘Missing’).

CCI

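### When only one of the three evaluators rates a photograph pair, that rating is left out of the primary analysis and the panel result is imputed from site, age and BMI alone

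*SAP*

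**What the plan says.** SAP 6.1.1.1 sets the majority rule: "Lift will be declared if at least two blinded evaluators indicate “Eyebrow Lift” for the comparator photograph". It then gives two rules for pairs that are not fully rated.

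- **Two or three 'Cannot Evaluate' ticks.** "In case at least two evaluators declare a photograph as not assessable", the instruction is that "the corresponding lift score over all evaluators will be set to missing for the primary analysis". No exception is made for the third rating.
- **One 'Cannot Evaluate' tick and a split.** If one evaluator cannot rate "and the other two evaluators disagree, the overall lift score will be set to" 'No Lift'.

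Missing panel results go to multiple imputation, expressly including those from unassessable photographs: "Missing data, including a missing primary endpoint assessment in subjects with unacceptable (i.e. unassessable) or missing photographs at baseline or Day 90, will be imputed". The model inputs are stated: "missing data in the primary endpoint (lift over all evaluators) is modelled via logistic regression based on input variables site, age and BMI". No evaluator-level rating is among them.

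SAP 6.4.1 covers missing evaluator results at Day 90 and Day 180 and agrees on the two-missing case: "If the result of two out of three evaluators is missing, the outcome of the subject will be set to missing". It differs on a split: one missing result with the other two in disagreement gives a missing outcome, not 'No Lift'. It does not say whether 'Cannot Evaluate' counts as a missing result. SAP 6.1.2 repeats the two-tick rule and the imputation for Day 180 but has no split rule.

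**The concern.** A single evaluator's rating is a strong predictor of the majority of three. After a lone 'No Lift', the panel can reach lift only if both other evaluators would have said lift. The imputation ignores this and gives the pair roughly the trial-wide lift rate. A pair with no lift vote can therefore carry a higher expected score than a fully rated pair with one lift vote and two no-lift votes, which always scores 0.

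Success requires a point estimate of at least 65% as well as a one-sided 95% Wilson lower bound above 50%. With about 50 subjects each pair is worth two percentage points, so the handling of one pair can decide whether the first condition is met. The current rule also needs a stronger missing-data assumption than necessary: that the panel result is missing at random given site, age and BMI, without conditioning on a rating that was actually collected.

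**Working it through.** **Inputs.** From SAP section 3: panel lift rate 72%, 40 evaluable subjects, about 50 enrolled, power at least 85%. From SAP 6.1.1.1: both success conditions and the scoring rules. Assumed, because the documents give no figure: three exchangeable evaluators with between-evaluator correlation ρ from 0 to 0.6, and site, age and BMI carrying little information, so that an imputed pair is credited with about the overall rate.

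**The plan's own figure.** At n = 40 the smallest passing count is 26 (65.0%, Wilson lower bound 52.0%). Exact binomial power at 72% is 87.6%, which meets the stated floor of 85%.

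**Expected score by rating pattern** (L = lift, NL = no lift, CE = 'Cannot Evaluate'):

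| Pattern | Expected score |
|---|---|
| CE, CE, NL | about 0.72 |
| CE, CE, L | about 0.72 |
| CE, CE, CE | about 0.72 |
| L, NL, NL | 0 |
| CE, L, NL | 0 under 6.1.1.1; about 0.72 under 6.4.1 if CE counts as missing |

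**What a lone rating implies.** Let θ be a pair's chance of a lift vote, with a beta distribution of mean p and ρ = 1/(a+b+1). Choose p so that 3E[θ²(1−θ)] + E[θ³] = 0.72. Then

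- P(panel lift | lone NL) = E[θ²(1−θ)] / E[1−θ]
- P(panel lift | lone L) = 1 − E[θ(1−θ)²] / E[θ]

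At ρ = 0, 3p² − 2p³ = 0.72 gives p = 0.651. The two probabilities are p² = 0.424 and 1 − (1−p)² = 0.878.

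| ρ | p | after lone NL | after lone L | variance with rating used ÷ (0.72 × 0.28) |
|---|---|---|---|---|
| 0 | 0.651 | 0.424 | 0.878 | 0.77 |
| 0.2 | 0.678 | 0.336 | 0.902 | 0.65 |
| 0.4 | 0.699 | 0.245 | 0.925 | 0.52 |
| 0.6 | 0.711 | 0.157 | 0.948 | 0.36 |

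Per pair, a lone NL is over-credited by 0.72 − 0.42 = 0.30 to 0.72 − 0.16 = 0.56 subjects, or 0.6 to 1.1 points at n = 50. A lone L is under-credited by 0.88 − 0.72 = 0.16 to 0.95 − 0.72 = 0.23 subjects.

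**Net effect if CE is uninformative.** At ρ = 0: 0.349 × (0.72 − 0.424) = 0.103 over-credited and 0.651 × (0.878 − 0.72) = 0.103 under-credited. The errors cancel. At ρ = 0.6: 0.289 × 0.563 = 0.163 and 0.711 × 0.228 = 0.162, equal within rounding.

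**Variance.** The imputation variance of such a pair is 1/0.77 = 1.3 to 1/0.36 = 2.8 times what it would be with the rating used. For the estimate as a whole this is small. With two such pairs in 50, recovering all their information would move the standard error only from √(0.72 × 0.28/48) = 6.48 points to √(0.72 × 0.28/50) = 6.35 points, and one rating recovers only part of that.

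**Why one pair can matter.** At n = 50 the 65% condition binds: 32/50 = 64.0% has a Wilson lower bound of 52.4% but fails. Take 32 lifts among 49 scored pairs and one pair with a lone NL:

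- as written, imputed at 32/49 = 0.653: 32.653/50 = 65.3%, condition met;
- with the rating used: (32 + 0.157)/50 = 64.3% to (32 + 0.424)/50 = 64.8%, not met.

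This is an illustration. A lone L close to the cut could work the other way.

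**The case against.** **No net bias is shown.** A reader might infer that the rule tilts the trial toward success. The documents do not support that. With uninformative CE the errors cancel, as computed above. Upward bias requires unassessable pairs to draw 'No Lift' more often than other pairs do, and nothing in either document says so. This objection stands.

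**The size cannot be stated.** It is tempting to say that one to three pairs with a lone 'No Lift' would raise the estimate by 0.6 to 3.4 points. That count leaves out lone 'Lift' ratings, which under the same model are 0.651/0.349 = 1.9 to 0.711/0.289 = 2.5 times as common. Protocol 11.2.1.1 also has the vendor accept baseline photographs before treatment, with retakes, which should keep such pairs few. This stands too.

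**The ranking of patterns is a general feature of imputation.** Any imputed outcome has a higher expected score than an observed failure, and the contrast with a split pair (CE, L, NL) depends on whether 6.1.1.1 or 6.4.1 governs. Both points are right. The contrast with L, NL, NL holds under either section, and what remains is that a relevant collected rating is ignored.

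**The lone rating may be unreliable.** If two physicians cannot assess an image, the third's rating may be mostly noise, and the overall rate would then be a sensible imputation. This is a fair limit on the 0.16 to 0.42 range, but the documents do not establish it.

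**Sensitivity analyses cover it.** SAP 6.1.1.2 plans a worst-case analysis, observed-case analyses and image-quality analyses. The worst case does score every lone 'No Lift' as a failure. But it does the same to lone 'Lift' pairs and dropouts, none of these analyses uses the lone rating, and none decides success.

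**Conclusion.** The point holds as a missing-data inefficiency with a possible bias of unknown sign. SAP 6.1.1.1, 6.1.2 and 6.4.1 discard the only rating available for a pair with two 'Cannot Evaluate' ticks or two missing results. At the 72% planning rate, with exchangeable evaluators and correlation 0 to 0.6, such a pair is credited with about 0.72 when its chance of panel lift is 0.16 to 0.42 after a lone 'No Lift', or 0.88 to 0.95 after a lone 'Lift'.

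If 'Cannot Evaluate' is uninformative, the cost is a small increase in variance. If these pairs lean to 'No Lift' more than others do, the estimate is biased upward; if they lean to 'Lift', downward. With no frequency in the documents, no net shift can be given, and the effect is nil if no pair has exactly one rating. It is still worth correcting because the 65% condition can turn on one pair.

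**What to change.** In SAP 6.1.1.1, 6.1.2 and 6.4.1, for pairs with exactly one rating, impute the absent evaluator ratings from the available rating plus site, age and BMI. Apply the two-of-three rule in each imputed dataset, and keep the planned pooling of estimates and Wilson bound. If the model does not converge, use the site-pooling fallback already in SAP 6.4.5. Make the change before the ratings are linked to treatment status.

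In the same edit, reconcile 6.1.1.1 ('No Lift') with 6.4.1 (missing) for a split with one 'Cannot Evaluate' or missing rating. State whether 'Cannot Evaluate' counts as a missing result, and carry the same rule into 6.1.2.

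Do not adopt the simpler asymmetric rule of scoring a lone 'No Lift' as 'No Lift' while still imputing a lone 'Lift' at the overall rate. With uninformative 'Cannot Evaluate' that rule credits 0.651 × 0.72 = 0.47 (ρ = 0) to 0.711 × 0.72 = 0.51 (ρ = 0.6) per such pair against a true 0.72, a downward bias of about 0.25 to 0.21 subjects per pair.

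The cost is SAP wording, slightly more imputation code and a somewhat larger model at about 50 subjects. No new data are needed, since Protocol 14.2.2 already has the photograph ratings transferred electronically to data management.
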